## Safety Set

The safety set will consist of all randomised subjects who received at least one dose of the IMP. The safety set will be used for the safety analyses.

## PK Set

See PKAP.

## ECG Set

The ECG set will consist of those subjects in the safety set that have at least one valid pre-dose ECG assessment and one valid post-dose assessment. An ECG assessment will be considered valid if it is based on at least two evaluable replicates with measurable QT and RR.

The analysis set for intensive cardiac assessment will be based on the intersection of the PK set and the ECG set. In addition, subjects on placebo will be included with plasma concentrations of PYR and PQP set to zero. Individual QTc/concentration pairs will be excluded from this set if the time of ECG and the time of blood sampling are too far apart: > 15min.

## **4.4 Subject Disposition**

All subjects will be included in the summary of subject disposition. This will present the overall number of subjects, the frequency and percentage of subjects randomized and treated, and who completed or discontinued from the study, along with reason for discontinuation.

Furthermore, the number and percentage of subjects in each analysis set will be tabulated. Discontinued subjects will be listed. Subject assignment to analysis sets will be listed. Screen Failures will not be listed or included in summary tables.

## **4.5 Demographic Characteristics**

Individual subject demographics (including age, sex, race and ethnicity) and body measurement data (height, body weight and body mass index and body weight group as defined above) at screening will be listed and summarized for the safety set. Height will be measured in centimetres and weight in kilograms, body mass index will be given in kg/m^2.

Other baseline characteristics with Beck depression inventory questionnaire will be listed only.

## 4.6 Inclusion and Exclusion Criteria

The inclusion and exclusion criteria text will be listed, as well as failed eligibility criteria for each randomised subject, if any.

## 4.7 Protocol Deviations

The final review of protocol deviations will be performed at the DRM prior to database lock. The protocol deviations will be listed.

## 4.8 Medical and Surgical History

Medical and Surgical history data will be coded using the Medical Dictionary for Regulatory Activities (MedDRA) dictionary Version 24.0 (or higher) and listed individually. Surgical history data will be listed separately. Medical and Surgical history data will be summarised using frequency and percentage by SOC and preferred term.

## 4.9 Study Drug Administration

Study drug administration data including treatment received, dose (unit), date and time of administration will be listed by subject.

## 4.10 Prior and Concomitant Medications

All prior and concomitant medications will be coded using the World Health Organization Drug Dictionary version 2022 (or higher) and will be listed individually. The frequency and percentage of prior and concomitant medications will be summarized by Anatomical Therapeutic Chemical and Preferred Name. Separate tables will be given for prior and concomitant medications. Prior medications are defined as those for which the end date and time is prior to the date, and time of first study drug administration. Concomitant medications are defined as those with start date and time on or after the date and time of first study drug administration and those with start date and time prior to the first study drug administration but with end date and time on or after the date and time of first study drug administration.

If medication dates are incomplete and it is not clear whether the medication was concomitant, it will be assumed to be concomitant.

## 4.11 Safety Analysis

Safety analyses will be performed on the safety set.

Safety analyses will include an analysis of all AEs, ECGs, clinical laboratory data, vital sign measurements and physical examination results and will be presented using descriptive statistics. No formal statistical analysis will be performed.

## Statistical Analysis Plan

### 4.11.1 Adverse Events

A Treatment Emergent Adverse Event (TEAE) is any adverse event that commences after the start of administration of study drug.

AEs with unknown start date/time will be assumed to be treatment-emergent unless the end date/time is known to be before the first administration of study drug. Otherwise missing or partial dates will be listed as such.

The incidence of TEAEs (after dosing) will be summarized using the safety set. The MedDRA dictionary Version 24.0 (or higher) will be used to classify all AEs reported during the study by System Organ Class (SOC) and Preferred Term. A summary of TEAEs including the incidence of subjects who experienced TEAEs (number and percentage of subjects) and incidence of TEAEs (number of events) will be presented for each treatment group and overall, by severity and by relationship to study drug.

Serious TEAEs (after dosing) and AEs leading to withdrawal will be summarized by SOC and Preferred Term for each treatment group and overall, and by relationship to study drug.

Subjects having multiple AEs within a category (e.g., overall, SOC and Preferred Term) will be counted once in that category. In each table, SOC and Preferred Term will be presented in descending order of overall incidence rate (alphabetical order will be used in case of equal rates).

All adverse events will be listed.

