## **7. TRIAL METHODOLOGY**

### **7.1 Medical history**

All clinically significant medical history (including any significant surgical procedures) must be recorded on the CRF for each participant. Each participant's full medical history will be obtained through direct questioning and the medical assessment at screening and will be updated at the day of admission (Day -1). If any clinically relevant observations or investigation results are detected prior to dosing, they will be recorded as medical history.

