## 8. ADVERSE EVENTS

The collection, evaluation and reporting of AEs/ARs arising from this clinical trial will be performed in accordance with:

- detailed guidance on the collection, verification and presentation of AE/AR reports arising from clinical trials on medicinal products for human use ('CT-3') (2011/C 172/01)
- International Conference on Harmonization (ICH) harmonised tripartite guideline on clinical safety data management: 'Definitions and standards for expedited reporting' E2A
- ICH harmonised tripartite guideline on Development Safety Update Report: E2F
- ICH guideline E2F 'Note for guidance on Development Safety Update Reports (DSUR)'.

It is the Investigator's responsibility to document and report all AEs that occur in the clinical trial. The period of observation for collection of AEs extends from the signing of the ICF until the final visit. Additionally, spontaneously reported Serious Adverse Events (SAEs) will be collected until 30 days after the final trial visit. SAEs experienced after this 30-day period will only be reported if the Investigator suspects a causal relationship with the trial drug.

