### 8.1 Definitions

An '**Adverse Event (AE)**' is any unfavourable and unintended sign (including an abnormal laboratory finding), symptom or disease temporally associated with the use of a medicinal product, whether considered related to it or not.

An AE may be:

- a new symptom or medical condition
- a new diagnosis
- an inter-current illness or an accident
- a worsening of a medical condition/disease(s) that existed before the start of the clinical trial
- the recurrence of a disease
- an increase in frequency or intensity of episodic diseases
- a change in a laboratory or other clinical test parameter
  - the criteria to determine whether an abnormal test result should be reported as an AE/AR are as follows. The abnormal test result:
    - is associated with accompanying symptoms, and/or
    - requires additional diagnostic testing or medical/surgical intervention
- an event that leads to a change in trial dosing outside of protocol-stipulated dose adjustments, or discontinuation from the trial, significant additional concomitant drug treatment, or other therapy, and/or

- considered an Adverse Event by the Investigator or Sponsor.

An AE does not necessarily include the following:

- an abnormal test that needs repeating, in the absence of any of the above conditions. Any abnormal test result that is determined to be an error does not require reporting as an Adverse Event
- surgical procedures themselves are not AEs; they are therapeutic measures for conditions that require surgery. The condition for which the surgery is required may be an AE/AR. Planned surgical measures permitted by the clinical trial protocol and the condition(s) leading to these measures are not AEs, if the condition leading to the measure was present before inclusion in the trial and has not worsened. In the latter case, the condition should be reported as medical history.

A '**Serious Adverse Event (SAE)**' is defined as any Adverse Event that fulfils any of the following criteria:

- it results in death
- it is life-threatening (the term 'life-threatening' in the definition of 'serious' refers to an event in which the participant was at immediate risk of death at the time of the event; it does not refer to an event which hypothetically might have caused death if it were more severe)
- it requires a hospitalisation\* or prolongs existing hospitalisation
- it results in persistent or significant disability/incapacity
- it is a congenital abnormality/birth defect

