## **8.2 Classification**

### **8.2.1 Assessment of severity**

The Investigator will assess the severity of AE/ARs using a categorical grading (mild, moderate or severe) with grading of individual AE/ARs based on global clinical assessment undertaken by an appropriately delegated Research Physician.

Changes in the severity of an AE/AR should be documented to allow an assessment of the AE/AR duration at each level of severity. AE/AR characterised as intermittent require documentation of the start and end of each incidence.

The table on the following page guides categorical grading of AE/ARs.

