### 2.2 Endpoints

#### Primary

- The incidence, severity and relationship of Treatment-Emergent Adverse Events (TEAEs).
- Proportion of participants with clinically significant changes in laboratory safety tests (haematology, biochemistry, coagulation and urinalysis).

- Proportion of participants with morphological and/or rhythm abnormalities on electrocardiogram (ECG).
- Proportion of participants with clinically significant changes in ECG time intervals (PR, QRS, QT and QTc intervals) and clinically significant changes against baseline Holter.
- Proportion of participants with clinically significant changes in vital signs (systolic blood pressure, diastolic blood pressure and pulse rate).

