**Table 1: Planned treatment arms and IMP administration**

Number of Participants	IMPs	Planned Dose (which depends on Body Weight [BW])	Number of Doses/ Dose Interval
16	PYR	540 mg (BW 50 kg - <65 kg); OR 720 mg (BW 65 kg or greater)	Single morning doses (fasted state) on D1, D2 and D3
	PQP	960 mg (BW 50 kg - <75 kg); OR 1280 mg (BW 75 kg or greater)	
8	PYR	540 mg (BW 50 kg - <65 kg); OR 720 mg (BW 65 kg or greater)	
	Placebo for PQP	N/A	
8	Placebo for PYR	N/A	
	PQP	960 mg (BW 50 kg - <75 kg); OR 1280 mg (BW 75 kg or greater)	
8	Placebo for PYR	N/A	
	Placebo for PQP	N/A	

[figure not shown]
Abbreviations: BW: body weight; D: day; IMP: investigational medicinal product; kg: kilograms; mg: milligrams; PQP: piperaquine; PYR: pyronaridine.

Participant screening will take place between Day -22 and Day -2. Each participant will receive verbal and written information, then sign the Informed Consent Form (ICF), before any screening procedures take place. Participants will be admitted on Day -1 and dosed once in the mornings of Day 1, Day 2 and Day 3. Participants in the sentinel group will be discharged on Day 7 and will return to the unit for outpatient assessments on Days 8, 15, 22. Non-sentinel group participants may be discharged on Day 5 and return for outpatient assessments on Days 6, 8, 15 and 22, provided there are no clinically significant safety and tolerability signals and the SRC are in agreement.

Final assessments will be carried out at the follow-up visit on Day 30 (+/-1 day). The trial Schedule of Assessments in protocol details all assessments that will take place during the trial. The study design features as well as the number of participants may be adapted according to the Adaptive Features. This trial will use a sentinel dosing strategy.

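### The TEAE definition rests on onset alone, so a continuous adverse event that starts before dosing and worsens on treatment can be left out of the TEAE tables, depending on how it is recorded

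*SAP*

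**What the plan says.** The definition in SAP 4.11.1 is: "A Treatment Emergent Adverse Event (TEAE) is any adverse event that commences after the start of administration of study drug". The same section presumes that events with an unknown start are treatment-emergent, but has no rule for an event already present at dosing that gets worse. The tables by severity and by relationship, and the serious-event table, are restricted to TEAEs. The table of events leading to withdrawal is not, and all adverse events are listed. TEAE incidence, severity and relationship is the first of five primary endpoint items in SAP 2.2.

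The protocol sets the collection window in Section 8: "The period of observation for collection of AEs extends from the signing of the ICF until the final visit". Screening opens well before dosing (SAP 3.1): "Participant screening will take place between Day -22 and Day -2".

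Four protocol rules bear on how a worsening is recorded:

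- Section 8.2.1: "Changes in the severity of an AE/AR should be documented to allow an assessment of the AE/AR duration at each level of severity". The next sentence there asks for the start and end of each incidence when an event is intermittent.
- Section 8.3 asks for one onset date and one resolution date per event.
- Section 8.1 includes among the things an adverse event may be "a worsening of a medical condition/disease(s) that existed before the start of the clinical trial" and "an increase in frequency or intensity of episodic diseases", together with anything the investigator or sponsor considers to be one.
- Section 7.1: "If any clinically relevant observations or investigation results are detected prior to dosing, they will be recorded as medical history".

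**The concern.** A definition that looks only at onset has no place for an event that straddles the first dose. Such an event could start mild on Day -1, become severe on Day 2, and appear in no TEAE row. If it became serious after dosing it could also miss the serious-TEAE table. The omission would lower the TEAE count in the trial's leading safety endpoint.

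The situation is plausible on the documents' own terms. Participants stop caffeine 48 hours before dosing (Protocol Table 11), and headache is listed for both drugs (Protocol Section 1 and Table 3). Inclusion criterion 2 lets the investigator include someone who vomited in the 24 hours before dosing, and gastrointestinal toxicity is the first of the three toxicities of focus in Protocol Section 1.

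The SAP already deals with the parallel case for medicines. Section 4.10 classes a medicine that was started before first dose and continued past it as concomitant. Adverse events that span first dose have no equivalent rule.

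**Working it through.** **Step 1: can a pre-dose event exist in a dosed participant?** Yes. Collection starts at consent, and screening may begin at Day -22, so the window is up to about 22 days long.

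**Step 2: does it count as a TEAE if it worsens after dosing?** That depends on the recording route. Take a mild event that starts on Day -1 and becomes severe on Day 2.

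| Recording route | Protocol section | Onset on the record | TEAE under SAP 4.11.1? |
|---|---|---|---|
| One continuous event with a severity change | 8, 8.2.1, 8.3 | Day -1 | No |
| Intermittent event, each incidence with its own start | 8.2.1 | Day 2 for the later incidence | Yes |
| Pre-dose finding as medical history, worsening as a new event | 7.1, 8.1 | Day 2 | Yes |

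The same clinical course therefore gives different answers. Section 8 (collection from consent) points to the first route and Section 7.1 to the third. The documents do not say which prevails.

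**Step 3: where does the event appear on the first route?** It is in the AE listing, and in the withdrawal table if it led to withdrawal. If it is a laboratory, ECG or vital-sign change, it is also assessed under the other four primary items. It is not in the TEAE tables by incidence, severity or relationship, nor in the serious-TEAE table. Protocol 10.3 foresaw summaries of all AEs, by maximum intensity, and of any SAEs. The corresponding SAP tables are narrower.

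**Step 4: weight of one uncounted participant, at planned arm sizes.**

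- Combination arm: 1/16 = 6.25 percentage points.
- Each other arm: 1/8 = 12.5 percentage points.

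SAP 3.2 says recruitment stopped at 37 and does not give the split. If, as an outer bound, all 40 - 37 = 3 missing participants fell in one arm, the figures would be 1/13 = 7.7 points or 1/5 = 20 points. The body-weight strata in SAP 4.1 are smaller again.

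**Step 5: the plan's own figure.** SAP 3.2 gives the chance of at least one case in 16 as 81% at a 10% event rate and 97% at 20%. Both reproduce from 1 - (1 - p)^16:

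- p = 0.10: 1 - 0.90^16 = 81.5%.
- p = 0.20: 1 - 0.80^16 = 97.2%.

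These figures do not depend on the TEAE wording. For illustration only, suppose a share w of true cases goes uncounted. The documents give no value for w; the range below is an assumption. The chance of at least one counted case is 1 - (1 - p(1 - w))^16.

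| w | p = 10% | p = 20% |
|---|---|---|
| 0 | 81.5% | 97.2% |
| 5% | 79.8% | 96.6% |
| 10% | 77.9% | 95.8% |
| 20% | 73.7% | 93.9% |
| 30% | 68.7% | 91.1% |

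**The case against.** The strongest reply is that nothing need be missed. Section 8.1 of the protocol accepts worsening as an adverse event in its own right, Section 7.1 sends clinically relevant pre-dose findings to medical history, and an intermittent complaint such as headache gets a new start at each incidence. Only a continuous, unresolved event that spans first dose and is kept as one record remains. Entry criteria make that uncommon: participants must be free of clinically significant illness in the four weeks before dosing. Safety analysis is descriptive (SAP 4.11), so no test or threshold changes, and the figures of 1/16 and 1/8 are the weight of any one participant in any table.

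Much of this stands. It makes the omission conditional and probably rare. It does not remove it, because Section 8 starts AE collection at consent and Section 8.2.1 follows severity within an event. Whether an event counts towards a primary endpoint should not turn on which form the site happens to use.

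Two stronger readings are tempting. A reader might infer that such an event is lost from the primary endpoint altogether. The two alternative recording routes, the full listing and the four other primary items do not support that. A reader might also infer that Section 8.1 confines worsening to conditions older than the trial. It does not: its list also covers episodic disease and investigator or sponsor judgement. What it lacks is an express statement for an ordinary event that starts between consent and first dose.

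**Conclusion.** The point holds in conditional form. Under the onset-only definition, a continuous event that begins between consent and first dose and worsens on treatment can be left out of the TEAE incidence, severity and serious-event tables. This follows if it is kept as a single record with a severity change. It does not follow if the worsening is entered as a new event or the event is recorded by incidence.

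For the events affected, the direction is towards under-counting. The presumption about unknown start dates works the other way, but it concerns missing dates and does not repair this gap. The number of affected events cannot be derived from the documents and is probably small in healthy volunteers. Each one would be visible in arms of this size: 6.25 points in 16 or 12.5 points in 8 at planned numbers. No stated figure in the plan changes. The correction is worth making because the rule serves the first primary endpoint and the data needed are already collected.

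**What to change.** In SAP 4.11.1, define a TEAE as any adverse event that starts after the first administration of study drug, or that starts before it and increases in severity or becomes serious afterwards. State that the severity tables use the maximum severity reached after first dose.

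Reconcile Protocol 7.1, 8, 8.1 and 8.2.1 on one question: does a worsening after dosing open a new record with its own onset date, or stay as a severity change within the existing one? With the wider definition the event counts on either route, but the answer is still needed so that it is not counted twice as an event.

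The cost is one sentence in the SAP, one on severity, and a recording clarification. Section 8.2.1 already requires severity changes to be documented, so no new data are needed. The change should be made before database lock and while the analysis team is still blinded.

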### 4.11.2 Laboratory Data

Clinical laboratory parameters (including blood chemistry, haematology, coagulation, urinalysis and other laboratory results) will be listed and abnormal parameters will be flagged and graded as high (H/x) or low (L/x) (where defined) according to reference ranges and CTCAE grade. Absolute (observed) values and changes from baseline (continuous variables) will be summarized for each parameter and scheduled time point by treatment group. The number of volunteers presenting out-of-range and clinically relevant values will be summarised by treatment group. The scheduled lab value will be used for summary analysis if repeated measurements are made at any time point.

For summary statistics, a lab value with "<" will be replaced with a numeric value by removing the "<" sign. In the listings, the values will be displayed as originally reported by the laboratory.

The mean and individual change from baseline value of ALT/AST/Bilirubin will be plotted by treatment group and by time-point. The number of subjects presenting out-of-range and clinically relevant values will be summarised.

The qualitative urinalysis data will be listed only.

Test Code	Test Unit	Range Low	Range High	Grade 1	Grade 2	Grade 3	Grade 4
ALT	IU/L	10	50	>ULN - 3.0 x ULN	>3.0 - 5.0 x ULN	>5.0 - 20.0 x ULN	>20.0 x ULN

